Identified risks for upadacitinib are summarized in the upadacitinib Investigator's Brochure⁸ and include: serious infections, opportunistic infections and tuberculosis (TB), and herpes zoster. Potential risks for upadacitinib include: malignancies, including lymphoma and non-melanoma skin cancer (NMSC), gastrointestinal (GI) perforations, major adverse cardiovascular events (MACE), hematologic changes (anemia, neutropenia, and lymphopenia), increased serum creatinine and renal dysfunction, hepatic events and increased hepatic transaminases, elevated creatine phosphokinase (CPK), embolic and thrombotic events (non-cardiac, non-central nervous system [CNS]), and fetal risks.

As of 15 December 2019, 171 healthy volunteers have received at least 1 dose of elsubrutinib; the most common side effect reported was headache, mild in severity.

As of 06 May 2020, from the Phase 2 RA and SLE studies, there are no identified safety risks for elsubrutinib or for ABBV-599 (elsubrutinib/upadacitinib) combination.

A detailed description of the preclinical pharmacology, metabolism, and toxicology datasets can be found in the elsubrutinib⁹ and upadacitinib⁸ Investigator's Brochures. The results of genetic toxicology testing indicate that elsubrutinib and upadacitinib are not genotoxic. Preclinical embryofetal development studies indicate that elsubrutinib and/or upadacitinib are embryotoxic, fetotoxic, and/or teratogenic.

Systemic lupus erythematosus patients are known to have an increased risk of thrombosis. Based on this and the potential risk of thrombosis with the use of JAK inhibitors, the use of estrogen-containing

contraceptives may further increase the risk of thrombotic events; therefore, the choice of contraceptive should be carefully considered.

In LTE Study M20-186, benefit/risk assessment of treatment groups for rollover may require subjects to be reassigned or discontinued based on the outcome of the unblinded interim analysis from the feeder Study M19-130 (See Section 4 Investigational Plan). Routine safety evaluations of all treatment groups will be performed. These include assessments of deaths, serious adverse events (SAEs), non-serious adverse events (AEs), withdrawals, and pregnancies, as well as routine monitoring by physical examinations, vital sign measurements, electrocardiograms, (ECGs), and clinical laboratory testing (hematology, chemistry, and urinalysis).

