3.4 Safety Endpoints

The following safety evaluations will be performed for the entire study duration as measures of safety and tolerability:

- AE monitoring
- Physical examinations
- Vital sign measurements
- ECGs
- Clinical laboratory testing (hematology, chemistry, and urinalysis)

Serious adverse events will be assessed at any dose that results in a death, inpatient hospitalization or prolongation of existing hospitalization, persistent or significant disability/incapacity, or a congenital anomaly (see Section 6.1 for more details).

The following areas of safety interest will be routinely assessed to identify any major safety findings related to immunosuppression or potential risks associated with the individual classes of therapy: serious and/or opportunistic infections, herpes zoster, active TB, malignancies (all types), adjudicated GI perforations, adjudicated cardiovascular events (e.g., MACE), anemia, neutropenia, lymphopenia, renal dysfunction, hepatic disorders, and adjudicated embolic and thrombotic events (non-cardiac, non-CNS) including venous thromboembolic events defined as pulmonary embolism and deep vein thrombosis (see Section 6.1 for more details).

Specific toxicity management measures will be utilized, as described in Section 6.2, for serious infections, serious GI events, cardiovascular events (MACE), malignancy, ECG abnormalities, and select laboratory abnormalities. In addition, a 30-day follow-up phone call from the last dose of study drug should occur to determine the status of any ongoing AEs/SAEs, or the occurrence of any new AEs/SAEs.

Additional safety monitoring measures include an independent Cardiovascular Adjudication Committee (CAC) (see Section 6.1) and an internal DMC (see Section 6.3).

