| Cardiovascular AE | Cardiovascular (Cardiac) AE eCRF Myocardial Infarction (MI) and Unstable Angina AE eCRF Heart Failure eCRF Cerebral Vascular Accident and Transient Ischemic Attack AE eCRF Embolic and Thrombotic Event (Non-cardiac, Non-central nervous system eCRF) |
| Hepatic Disorders AE | Hepatic Supplemental Local Labs eCRF Hepatic Supplemental Procedure eCRF (Non-SAE Non-Protocol Diagnostic/Therapeutic Procedures) Hepatic Abnormal Laboratory Value Supplemental |
| Herpes zoster | Herpes zoster eCRF |
| Elevated CPK | Increased CPK Supplemental eCRF |
| Renal Dysfunction | Renal Supplemental Local Labs eCRF Renal Supplemental Procedure eCRF Renal Abnormal Laboratory Value Supplemental eCRF |
| COVID-19 Infection | COVID-19 Supplemental Signs/Symptoms eCRF COVID-19 Status Form eCRF |
| Death | Death eCRF |

AE = Adverse event; COVID-19 = coronavirus disease 2019; CPK = Creatine phosphokinase; eCRF = Electronic case report form; SAE = Serious adverse event

If an AE, whether associated with study drug or not, meets any of the following criteria, it is to be reported to AbbVie clinical pharmacovigilance as an SAE within 24 hours of the site being made aware of the SAE (refer to Section 4.3 of the Operations Manual for reporting details and contact information):

| Death of Subject | An event that results in the death of a subject. |
|--|--|
| Life-Threatening | An event that, in the opinion of the investigator, would have resulted in immediate fatality if medical intervention had not been taken. This does not include an event that would have been fatal if it had occurred in a more severe form. |
| Hospitalization or Prolongation of Hospitalization | An event that results in an admission to the hospital for any length of time or prolongs the subject's hospital stay. This does not include an emergency room visit or admission to an outpatient facility. |
| Congenital Anomaly | An anomaly detected at or after birth, or any anomaly that results in fetal loss. |

Persistent or Significant Disability/Incapacity

An event that results in a condition that substantially interferes with the activities of daily living of a study subject. Disability is not intended to include experiences of relatively minor medical significance such as headache, nausea, vomiting, diarrhea, influenza, and accidental trauma (e.g., sprained ankle).

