The following adverse events of special interest (AESI) will be routinely monitored during the study:

- Serious infections
- Opportunistic infections
- Herpes zoster
- Active TB
- Malignancy (all types)
- Adjudicated GI perforations
- Adjudicated cardiovascular events (e.g., MACE)
- Anemia
- Neutropenia
- Lymphopenia
- Renal dysfunction
- Hepatic disorders
- Adjudicated embolic and thrombotic events (non-cardiac, non-CNS) including venous thromboembolic events defined as pulmonary embolism and deep vein thrombosis.

Adverse Event Severity and Relationship to Study Drug

Investigators will rate the severity of each AE according to the National Cancer Institute (NCI) Common Terminology Criteria for Adverse Events (CTCAE) version 5, which can be accessed at: https://ctep.cancer.gov/protocoldevelopment/electronic_applications/docs/ctcae_v5_quick_reference_8.5x11.pdf.

If no specific grading criteria are provided for the reported event, then the event should be as follows:

- Mild (Grade 1): asymptomatic or mild symptoms; clinical or diagnostic observations only; intervention not indicated;
- Moderate (Grade 2): minimal, local or noninvasive intervention indicated; limiting
 age-appropriate instrumental activities of daily living (ADL) (instrumental ADL refer to preparing
 meals, shopping for groceries or clothes, using the telephone, managing money, etc.);
- Severe (Grade 3 5):
 - Grade 3: severe or medically significant but not immediately life-threatening; hospitalization or prolongation of hospitalization indicated; disabling; limiting self-care ADL (self-care ADL refers to bathing, dressing and undressing, feeding self, using the toilet, taking medications, and not bedridden);

- Grade 4: Life-threatening consequences; urgent intervention indicated;
- Grade 5: Death related to AE.

The investigator will use the following definitions to assess the relationship of the AE to the use of study drug:

| Reasonable Possibility | After consideration of factors including timing of the event, biologic plausibility, clinical judgment, and potential alternative causes, there is sufficient evidence (information) to suggest a causal relationship. |
|------------------------------|--|
| No Reasonable Possibility | After consideration of factors including timing of the event, biologic plausibility, clinical judgment, and potential alternative causes, there is insufficient evidence (information) to suggest a causal relationship. |

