| | A positive result for HBV DNA PCR testing in these subjects will require immediate interruption of study drug (per local guidelines) and a hepatologist consultation should occur within 1 week for recommendation regarding subsequent treatment. |
| Serum Creatinine | • If serum creatinine is > 1.5 × the baseline value and > ULN, repeat the test for serum creatinine (with subject in an euvolemic state) to confirm the results. If the results of the repeat testing still meet this criterion then interrupt study drug and re-start study drug once serum creatinine returns to ≤ 1.5 × baseline value and ≤ ULN. |
| | If confirmed new serum creatinine ≥ 2 mg/dL, interrupt study drug and re-start study drug once serum creatinine returns to normal reference range or its baseline value. |
| | For the above serum creatinine elevation scenarios, complete supplemental renal eCRF(s). |

| Laboratory Parameters | Toxicity Management Guidelines |
|-----------------------------------|--|
| Creatine Phosphokinase (CPK) | CPK and aldolase will be measured at every visit, but results will be blinded to sites and subjects, as CPK elevation is a known class effect of JAK inhibitors and the results could be unblinding to the sites. If symptomatic myositis is suspected, the site may send a request to the AbbVie TA MD for CPK and/or aldolase results to be unblinded. Request must be approved by the AbbVie TA MD. |
| | If confirmed CPK ≥ 4 × ULN accompanied by symptoms suggestive of myositis or rhabdomyolysis, interrupt study drug, complete supplemental CPK eCRF, and contact the AbbVie TA MD. |
| Lymphocyte Count Decreased | • If confirmed Grade 4 (< 200/mm³) by repeat testing with new sample, interrupt study drug dosing until lymphocyte count returns to at least Grade 2 (< 800 to 500/mm³) or its baseline value. |
| White Blood Count Decreased | If confirmed Grade 4 (<1000/mm³) by repeat testing with new sample, interrupt study drug dosing until white blood cell count returns to at least Grade 2 (< 3000 to 2000/mm³) or its baseline value. |
| Urine Protein to Creatinine Ratio | If > 2 g/day equivalent (2 mg/mg), repeat by testing with new sample, and if confirmed, a renal biopsy will be required. |
| | If Class IV lupus nephritis is confirmed, subject must be permanently discontinued from study drug. |

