7.4 Statistical Analyses for Safety

All safety analyses will be performed on the Safety Analysis Set.

All treatment-emergent adverse events (TEAEs), SAEs, AEs leading to discontinuation, and AESI will be collected during the study. A TEAE is defined as an event with onset or worsening after the first study dose of study drug and within 30 days after the last dose of study drug administration. The number and percentages of subjects experiencing TEAEs will be tabulated using the Medical Dictionary for Drug Regulatory Activities (MedDRA®) System Organ Class (SOC) and preferred term (PT). Summaries (including percentages and events per 100 patient-years) of SAEs, deaths, AEs leading to discontinuation, and AESI will be provided as well. For selected laboratory and vital sign parameters, mean change from Baseline and the percentage of subjects with evaluations meeting pre-defined criteria for Potentially Clinically Important values will be summarized.

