Appendix B. Definition of Adverse Events of Special Interest

Adverse Events of Special Interest (AESI) will be identified using the following search criteria:

AESI	Type of MedDRA Query	Broad or Narrow Search	SMQ/CMQ Search Criteria
Serious Infections	CMQ		"Infections" – Subset for SAEs
Opportunistic Infection excluding Tuberculosis and Herpes Zoster	CMQ		"Opportunistic Infection" excluding Tuberculosis and Herpes Zoster CMQ
Herpes Zoster	CMQ		"Herpes Zoster"
Active Tuberculosis	CMQ		"Active Tuberculosis"
Possible Malignancy	SMQ	Narrow	"Malignancies"
Malignancy	SMQ	Narrow	"Malignant Tumours"
Malignancies excluding NMSC	SMQ	Narrow	"Malignant Tumours" removing NMSC output
Non-Melanoma Skin Cancer (NMSC)	SMQ	Narrow	"Skin Malignant Tumours" removing Melanoma CMQ
Adjudicated GI perforations			Based on adjudicated results (the identification of events to be adjudicated are described in the GI Perforation charter)
Adjudicated cardiovascular events: MACE*		Output from CAC	
Cardiovascular Death			
Non-fatal Myocardial Infarction			
Non-fatal Stroke			
Undetermined/Unknown Cause of Deaths			
Other Cardiovascular events			
Anemia	CMQ		"Non-Hemolytic and Non-Aplastic Anemias"
Neutropenia	CMQ		"Hematological Toxicity – Neutropenia"
Lymphopenia	CMQ		"Hematological Toxicity - Lymphopenia"

AESI	Type of MedDRA Query	Broad or Narrow Search	SMQ/CMQ Search Criteria
Renal dysfunction	SMQ	Narrow	"Acute Renal Failure"
Hepatic disorders	SMQ	Narrow	"Drug Related Hepatic Disorders"
Adjudicated Thrombotic Events: VTE**	Output from CAC		
Deep Vein Thrombosis			
Pulmonary Embolism			
Other Venous Thrombosis			

* MACE: Major Adverse Cardiovascular Events, defined as cardiovascular death, non-fatal myocardial infarction and non-fatal stroke.

** VTE: Venous thromboembolic events, defined as deep vein thrombosis (DVT) and pulmonary embolism (PE) (fatal and non-fatal).

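### CPK elevation is a named upadacitinib risk and JAK class effect but has no AESI entry, so CPK and muscle events get no grouped AE count, exposure-adjusted rate or AESI listing

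*Protocol*

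**What the plan says.** Protocol 2.2 divides upadacitinib's risks into identified and potential ones. The potential group includes "hepatic events and increased hepatic transaminases, elevated creatine phosphokinase (CPK), embolic and thrombotic events". In Section 6.2, Table 4 explains why CPK and aldolase results are withheld from sites and subjects: "as CPK elevation is a known class effect of JAK inhibitors and the results could be unblinding to the sites". In Section 6.1, Table 3 requires an "Increased CPK Supplemental eCRF" when elevated CPK is reported.

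Section 3.4 introduces the areas of safety interest as serving to find major safety findings from immunosuppression or "potential risks associated with the individual classes of therapy: serious and/or opportunistic infections, herpes zoster, active TB, malignancies (all types", and then continues the list. CPK is not in it. Section 6.1 states "The following adverse events of special interest (AESI) will be routinely monitored during the study" and gives 13 entries; none is CPK elevation, myositis or rhabdomyolysis. SAP Appendix B opens with "Adverse Events of Special Interest (AESI) will be identified using the following search criteria" and has no CPK or muscle query.

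On output, Protocol 7.4 promises: "Summaries (including percentages and events per 100 patient-years) of SAEs, deaths, AEs leading to discontinuation, and AESI will be provided as well". SAP 9.2.2, 9.2.6 and 9.2.9 add an AESI line in the AE overview, AESI tables by SOC and PT, and AESI listings.

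**The concern.** The list in 3.4 gives the risks of each drug class as one of its purposes, and the protocol itself names CPK elevation as such a risk. Leaving it out, with no reason given, makes the AESI list inconsistent with the risk section behind it.

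What is at stake is how the primary objective, longer-term safety, is reported. An AESI entry pools related preferred terms under one search definition and carries the percentages, exposure-adjusted rates and listings above. Without one, reports of raised CPK, myositis and rhabdomyolysis are spread over separate preferred terms. A reader then has to assemble the category by hand, choosing the terms after the data are seen. Three of the four LTE regimens contain upadacitinib, as do five of the six analysis sequences (Groups 1, 2, 4, 5a and 5b).

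**Working it through.** No power, alpha or event figure is involved, and the plan states no number to reproduce. The check compares the lists and then traces each planned CPK output.

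**Step 1: risks in Protocol 2.2 against the AESIs in 6.1.** Identified risks: serious infections, opportunistic infections and TB, herpes zoster (3). Potential risks: malignancy, GI perforation, MACE, hematologic changes, creatinine/renal, hepatic, CPK, embolic/thrombotic, fetal (9). Total 3 + 9 = 12. All 3 identified and 7 of the 9 potential risks map to an AESI, which makes 10. The other 12 − 10 = 2 are CPK and fetal risk. Pregnancy has its own reporting route in Section 6.1.

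**Step 2: the laboratory-based risks only.**

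| Risk in Protocol 2.2 | Selected variable in SAP 9.3 | AESI in Protocol 6.1 | Row in SAP Appendix B |
|---|---|---|---|
| Anemia | hemoglobin | yes | yes |
| Neutropenia | neutrophils | yes | yes |
| Lymphopenia | lymphocytes | yes | yes |
| Creatinine/renal | creatinine | yes | yes |
| Hepatic/transaminases | ALT, AST | yes | yes |
| CPK | CPK | **no** | **no** |

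Five of the six have both a laboratory analysis and an AESI row. CPK has only the laboratory analysis.

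**Step 3: Table 3.** Seven event types need a supplemental report. Four are AESIs (cardiovascular, hepatic, herpes zoster, renal). Two have their own lines in the AE overview of SAP 9.2.2 (COVID-19, deaths). That leaves 7 − 4 − 2 = 1, elevated CPK, with dedicated data collection and no dedicated AE output.

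**Step 4: what the SAP does plan for CPK.**

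- Section 9.3: summaries by visit, shift tables, the number and percentage of subjects per group with a potentially clinically important value, and a listing of all observations for those subjects.
- Sections 9.2.1 and 9.2.3: any reported CPK or muscle TEAE, under its own preferred term.
- Section 9.2.4: TEAE rates per 100 subject-years.
- Sections 9.2.5 and 9.2.9: serious events, and events leading to discontinuation, in tables and listings.

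Not planned: a pooled CPK/muscle AE count, a rate for that category, or an AESI listing of it.

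**Step 5: how far the existing outputs fill the gap.** Sites do not see CPK values unless a request is approved (Table 4). Under Section 6.1 a laboratory abnormality becomes an AE only under certain conditions, one of which is the investigator's own judgment. Symptom-free elevations may therefore not reach the TEAE tables. The count in SAP 9.3 rests on CTCAE version 4.03 with a cut-off worded as above Grade 3 or above Grade 4; read literally, that leaves out Grade 3 itself. It also does not connect values with muscle symptoms.

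**The case against.** The strongest reply is that the documents nowhere promise one AESI per risk. Section 3.4 speaks of major findings, fetal risk is absent too, and the choice of AESIs is largely the sponsor's. The next paragraph of 3.4 sends select laboratory abnormalities to Section 6.2, where CPK has its own rule. Much of this stands: a reader might infer that the list breaches a commitment, and the documents do not support that. But the same section lists anemia and lymphopenia, and no reason is given for treating CPK differently. Section 6.2 governs management of subjects and is silent on what is tabulated.

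A second reply is that laboratory values are the better route, because an AE query will miss elevations that sites cannot see. This also stands in part, and it is why the fix pairs the AE row with a laboratory count. It does not explain why the other five laboratory-based risks get both outputs.

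A third reply is that AESI status may not deliver a category rate: SAP 9.2.6 specifies only SOC and PT, and the overview in 9.2.2 has one combined AESI line. The rate rests on Protocol 7.4. This is fair, so the fix asks for the rate explicitly. SAP 9.2.2 also allows further AE tabulations on advice from Clinical and Safety, but that is discretionary and not prespecified.

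**Conclusion.** The omission is confirmed in both documents. CPK is the only laboratory-based risk in Protocol 2.2 without an AESI entry, and CPK and muscle events have no grouped AE count, exposure-adjusted rate or AESI listing. The change is worth making because safety is the primary objective and the data are already collected.

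Two stronger readings should be resisted. A reader might infer that CPK goes unreported; SAP 9.3 and the general TEAE tables show that it does not. A reader might also want the number of events lost from view. The documents give no rate of CPK or muscle events, one regimen has no JAK inhibitor, and treatment groups may be discontinued, so no count can be supported. The size of the point is one missing category out of the six laboratory-based risks. The conclusion assumes only that the lists are complete as printed.

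**What to change.** Add CPK elevation to the lists in Protocol 3.4 and 6.1. Add a row to SAP Appendix B combining the blood CPK increased term with a myopathy/rhabdomyolysis query. State in the SAP that this row is reported by treatment group as n, percentage, events per 100 patient-years and a listing.

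Beside it, show the number of subjects with any post-baseline central-laboratory CPK ≥ 4 × ULN. Label this a descriptive laboratory cut-off. It should not be presented as the Table 4 trigger, which also requires confirmation and symptoms suggestive of myositis or rhabdomyolysis. No change to clinical management is implied. If the sponsor prefers to leave CPK out of the AESIs, the SAP should say why laboratory reporting is enough.

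Cost: one line in each of two protocol lists, one or two rows in Appendix B and its outputs, and a slightly higher total AESI count. The AEs, the supplemental eCRF and the central CPK values are already collected.

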4 INVESTIGATIONAL PLAN

4.1 Overall Study Design and Plan

This is a multicenter, double-blind LTE Phase 2 study to investigate the longer-term safety and efficacy of elsubrutinib and upadacitinib given alone or as the ABBV-599 (elsubrutinib/upadacitinib) combination in subjects with moderately to severely active SLE. The study population will consist of approximately 195 to 260 individuals with moderately to severely active SLE despite standard of care therapy.

Subjects who participated in Study M19-130 may be offered the opportunity to consent for this study. The number of subjects participating in this study will not be greater than the number randomized into Study M19-130. Subjects discontinuing study drug prematurely in Study M19-130 are not eligible to participate in the LTE study.

In Study M19-130, subjects were randomized in a 1:1:1:1:1 ratio to one of 5 treatment groups:

- Elsubrutinib 60 mg once a day (QD) and upadacitinib 30 mg QD (projected n = 65)
- Elsubrutinib 60 mg QD and upadacitinib 15 mg QD (projected n = 65)
- Elsubrutinib 60 mg QD and upadacitinib placebo QD (projected n = 65)
- Elsubrutinib placebo QD and upadacitinib 30 mg QD (projected n = 65)
- Elsubrutinib placebo QD and upadacitinib placebo QD (projected n = 65)

Prior to the planned Study M19-130 Interim Analysis, qualified subjects entering into LTE Study M20-186 stayed in their original treatment group from Study M19-130 if on an ABBV-599 (elsubrutinib/upadacitinib) combination, elsubrutinib 60 mg monotherapy, or upadacitinib 30 mg monotherapy. Those originally assigned to the placebo group in Study M19-130 were randomized centrally in a 1:1 ratio to the 2 ABBV-599 (elsubrutinib/upadacitinib) combination treatment groups.

Prior to the planned Study M19-130 Interim Analysis, there were 4 treatment groups in this LTE study:

- Group 1: Elsubrutinib 60 mg QD and upadacitinib 30 mg QD
- Group 2: Elsubrutinib 60 mg QD and upadacitinib 15 mg QD
- Group 3: Elsubrutinib 60 mg QD and upadacitinib placebo QD
- Group 4: Elsubrutinib placebo QD and upadacitinib 30 mg QD

A planned unblinded interim analysis for Study M19-130 was scheduled when 50% of the planned subjects completed their Week 24 assessments. The objective of this analysis was to reassess the treatment regimens in Study M19-130 and the benefit/risk for rollover into LTE Study M20-186.

The Study M19-130 Interim Analysis was performed by an independent team at AbbVie that was separate and apart from the blinded study team for Study M19-130. The M19-130 study team will remain blinded through the Study M19-130 Week 24 Primary Analysis.

An Interim Unblinding Plan (IUP) was developed separately describing the analyses to be performed and included execution logistics, an unblinded analysis team, and the data chain of custody to protect the integrity of the study.

An Internal Executive Review Committee (IERC) reviewed the interim unblinded results as specified in the IERC charter and decided which treatment group(s) should be continued in Study M19-130 and for rollover into LTE Study M20-186. Study sites and subjects remained blinded to treatment assignment in Study M19-130 and LTE Study M20-186 throughout the studies.

Based on the benefit/risk assessment of the planned Study M19-130 Interim Analysis, subjects in 1 or more groups of LTE Study M20-186 may be discontinued. Subjects in any discontinued group(s) should return for a Premature Discontinuation (PD) visit and have a follow-up phone call 30 days after the last study drug dose.

Subjects originally assigned to the placebo group in Study M19-130 will be rolled over and will be randomized to an active treatment group in LTE Study M20-186.

[figure not shown]
This study includes a 56-week double-blind treatment period with study visits conducted at Weeks 48, 56, 64, 72, 80, 88, 96, and 104 (from the Baseline visit of Study M19-130), and a subsequent telephone follow-up call 30 days after the last visit to determine the status of any ongoing AEs/SAEs or the occurrence of any new AEs/SAEs. The plan is to extend the trial if data support the safety and efficacy endpoints during the 56-week LTE study duration.

An interim analysis for LTE Study M20-186 may be performed to aid data interpretation and to facilitate interactions with regulatory authorities.

The schematic of the study is shown in Figure 1. Further details regarding study procedures are located in the Operations Manual (Appendix H). See Section 5 for information regarding eligibility criteria.

Figure 1. Study Schematic

QD = once daily

